#### 1.0 Introduction

#### 1.1 Device Name (working name)

Rapid SARS-CoV-2 Antigen Test (MP Biomedicals, LLC [name]).

#### 1.2 Intended Use

The MP Biomedicals Rapid SARS-CoV-2 Antigen Test is an immunochromatography based one step in vitro test intended to detect nucleocapsid antigen from the SARS-CoV-2 virus that causes COVID-19. It is designed for over the counter (OTC) rapid qualitative determination of SARS-CoV-2 virus antigen in anterior nasal swabs from individuals within 7 days of symptom onset or without symptoms or other epidemiological reasons to suspect COVID-19 infection. This test is for non-prescription home use with self-collected anterior nasal swab specimens directly from individuals aged 14 years and older or with adult-collected anterior nasal samples directly from individuals aged 2 years or older.

#### 1.3 Background

Coronavirus disease (COVID-19) is a disease caused by a newly discovered coronavirus, severe acute respiratory syndrome coronavirus 2 (SARS-CoV-2)¹. The SARS-CoV-2 is a \$\beta\$-coronavirus, which is enveloped non-segmented positive-sense RNA virus 2². It is spread by human-to-human transmission via droplets or direct contact, and infection has been estimated to have mean incubation period of 6.4 days and a basic reproduction number of 2.24–3.58. Among patients with pneumonia caused by SARS-CoV-2, fever was the most common symptom, followed by cough³. On 11 March 2020, the COVID-19 outbreak was characterized as a pandemic by the WHO⁴. Since then, over 70 million people worldwide have been infected with the virus with over 1.5 million deaths attributed to the virus⁵. Laboratory testing for SARS-CoV-2 is currently being performed to determine if an individual has active infection via detection of viral RNA or if an individual has an immune response to the virus from a previous infection via detection of antibodies.

Specimen collection is a crucial first step in the evaluation of an individual's SARS-CoV-2 infection status. The goal of this project is to evaluate a rapid SARS-CoV-2 antigen test for over the counter (OTC) use. Study subjects under EDP supervision, either in-person or via video conference, will collect and test anterior nasal swab samples and a Study Representative will collect and ship a second nasopharyngeal swab sample for comparator PCR testing. The Rapid SARS-CoV-2 Antigen Test

collection and testing methodology is viewed as a convenient and inexpensive method to test clinical specimens for SARS-CoV-2 and OTC access will improve the availability of COVD-19 testing.

#### 1.4 Principles of the Device

The COVID-19 Antigen Rapid Test Device detects SARS-CoV-2 viral antigens through visual interpretation of color development. Anti-SARS-CoV-2 antibodies are immobilized on the test region of the nitrocellulose membrane. Anti-SARS-CoV-2 antibodies conjugated to colored particles are immobilized on the conjugated pad. A sample is added to the extraction buffer which is optimized to release the SARS-CoV-2 antigens from specimen. During testing, the extracted antigens bind to anti-SARS-CoV-2 antibodies conjugated to colored particles. As the specimen migrates along the strip by capillary action and interacts with reagents on the membrane, the complex will be captured by the anti-SARS-CoV-2 antibodies at the test region. Excess colored particles are captured at the internal control zone. The presence of a colored band in the test region indicates a positive result for the SARS-CoV-2 viral antigens, while its absence indicates a negative result. A colored band at the control region serves as a procedural control, indicating that the proper volume of specimen has been added and membrane wicking is working. (See Appendix 6).

# 2.0 Scientific Objectives

#### 2.1 Study Rationale

Traditional specimen collection techniques used in conjunction with respiratory infectious agent identification, for examples nasopharyngeal (NP) swabbing or aspiration, are often uncomfortable for the patient. Anterior nasal (AN) swab samples have provided a more comfortable sampling alternative to NP swabs that is also less technically challenging. With ease of use and convenience for OTC home specimen collection with the Rapid SARS-CoV-2 Antigen Test, the patient experience may lead to better patient sampling for SARS-CoV-2 testing.

#### 2.2 Study Objectives

The objective of the study is to evaluate the feasibility of using Rapid SARS-CoV-2 Antigen Test detection of SARS-CoV-2 virus in OTC home use. The presence of SARS-CoV-2 virus will be confirmed by PCR methodology. Testing will be performed with EUA PCR tests. The acceptance criteria for this study is Positive Percent Agreement (PPA) greater than or equal to eighty percent and Negative Percent Agreement (NPA) greater than or equal to ninety-eight percent).

# 3.0 Study Materials

EDP Biotech Corp. will obtain the Rapid SARS-CoV-2 Antigen Test kits and swab collection supplies, and Diversified Medical Health (DMH) Premier Laboratories will obtain the PCR reagents and materials to perform the testing from the respective manufacturers. EDP Biotech Corp. will maintain proper storage conditions of all reagents per the manufacturers' product package inserts.

#### 3.1 Specimen Collection Materials/Equipment

All Rapid SARS-CoV-2 Antigen Test materials are ready for use as per Manufacturer's instructions. The materials will be used prior to expiration dating.

Table 1 Rapid SARS-CoV-2 Antigen Test Materials

Material	Manufacturer	Catalog Number	Storage
Rapid SARS-	MP Biomedicals		Ambient
CoV-2 Antigen	Solon, OH USA		(15-25°C)
Test Card			
(sealed foil			
pouch)			
Sterile swab	Zhejiang Gongdong		Ambient
	Medical Technology		$(15-25^{\circ}C)$
	Co., Ltd		
	[name],		
	[name]		
	Taizhou, Zhejiang,		
	P.R.China		
Extraction tube	MP Biomedicals		Ambient
	Solon, OH USA		(15-25°C)
Extraction	MP Biomedicals		Ambient
solution bottle	Solon, OH USA		(15-25°C)
Instructions for	MP Biomedicals		Ambient
use (IFU)	Solon, OH USA		(15-25°C)
Tube stand	MP Biomedicals		Ambient
	Solon, OH USA		(15-25°C)

#### 3.2 PCR Collection Materials

Nasopharyngeal swab specimens will be evaluated for the presence of SARS-CoV-2 RNA with the DMH Premier

CDC 2019-nCoV Real-Time RT-PCR Diagnostic Panel (CDC) at their Premier Laboratory facility in Greenville, SC (see Appendices 1 and 2).

Material	Manufacturer/ Vendor	Catalog Number	Storage 1
Sterile Swab	Premier		Ambient (15-25°C)
Tube Label	Premier		Ambient (15-25°C)
Collection Tube with Universal Transport Media	Premier		Ambient (15-25°C)
Collection Instructions	Premier		Ambient (15-25°C)
Biohazard bag with absorbent pad	Premier		Ambient (15-25°C)
Shipping box with cold pack	Premier		Ambient (15-25°C)

Table 2- PCR Collection and Shipping Materials for Nasopharyngeal swab Specimens:

#### 3.3 Instrumentation

Testing of collected respiratory specimens associated with this protocol will be performed with the following equipment:

- 3.2.1 For nasal swab specimens at DMH Premier Laboratory:
- QuantStudio 12 K Flex Real-Time PCR System (Thermo Fisher Scientific)

#### 3.4 Computer Hardware and Software

For this study, results will be analyzed using:

- > PC Computer Platform.
- ➤ Microsoft Office Excel, version 2003 (or higher).

#### 3.5 Collection/Storage/Transfer of Data Files

All data will be collected and stored by EDP Biotech Corp. using its established laboratory information system (LIS) upon completion of the initial testing or resolution of incomplete or disqualified runs. Results will be compiled as a specimen log as part of the clinical study documentation.

If applicable, all original instrument data printouts will be maintained as part of the study records. Additionally, records of personnel performing all assays, all instruments, reagent and control lots used for each assay run will be maintained.

Note: All required ancillary equipment and materials for the study are specified in appropriate Standard Operating Procedures (SOPs), along with the instrument

operator's manuals and reagent instructions for use (package insert), either at DMH Premier Laboratories or EDP Biotech Corp.

# 4.0 Study Design

This is a clinical study to evaluate the feasibility of using anterior nasal (AN) swabs on Rapid SARS-CoV-2 Antigen Test kits for OTC use in symptomatic and asymptomatic individuals following recommendations from the FDA's November 9, 2021 Template for Developers of Molecular and Antigen Diagnostic COVID-19 Tests for Home Use, Sections J 8, 9. EDP Biotech Corp. will recruit subjects for a clinical study through the internet as well as by referral throughout the United States. Rapid SARS-CoV-2 Antigen Test anterior nasal specimen collection and testing will be done under the supervision of EDP Biotech Corp. or designee in person. Standard of care (SOC) comparator NP samples will be collected at least 15 minutes prior to Ag samples with at least 15 minutes between nasal collections including collections that may occur prior to study enrollment. Comparator SOC samples will be collected first by qualified personnel at a study site or physician's office using an FDA authorized nasopharyngeal swab collection kit and SARS-CoV-2 molecular assay. An observed usability study will be conducted prior to this clinical evaluation study. Comparator SOC nasopharyngeal swab specimens will be analyzed at Premier Laboratories according to this protocol and specific assay standard operating procedure (SOP) instructions. The data collected in study may be submitted as a regulatory filing to the US FDA or other agencies. All specimens will be collected from participating consenting subjects. Additional testing of the specimens for research purposes may be performed. A single randomly generated non-repeating study ID number will be assigned to subject or subject and tester if a parent or legal guardian is testing a 2 to 13 year old and this study ID number will be applied to all informed consent and authorization forms, assent forms, tester information form, subject information form, user comprehension assessment, and any other documents associated with each valid Rapid SARS-CoV-2 Antigen test result.

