#### 4.3 Specimen Collection

Each study volunteer who agrees to participate in the study will be asked to complete an Informed Consent Form (Appendix 7). A parent or guardian will need to consent for subjects under 18 years old. Study subjects between the ages of 7 and 13 years old will be asked to complete an age-appropriate Assent form (Appendix 8). Study subjects between ages 14 and 17 will complete the assent portion of the Informed Consent Form (Appendix 7). Minors between the ages of 2 and 13 years old will have their samples collected and tested by a parent or legal guardian. Minors between the ages of 14 and 17 will collect and test their own samples without interference from their parents or legal guardians. Specimens will be collected and tested only after the Informed Consent form is completed.

Each testing participant will be asked to complete a tester information form assessing basic demographics and socio-economic questions (Appendix 3). Each subject being tested will be asked to complete a subject information form describing any symptoms of respiratory illness and/or resent exposure to confirmed COVID-19 positive individuals within the last two weeks (Appendix 4). If the tester is self-collecting, then they skip the second half of the subject information form as indicated on the form due to redundancy of demographic and socio-economic information recorded on the tester information form. Subjects and testers will be observed by EDP Biotech Corp. personnel or designees during sample collection and testing process in person. The same unique study ID number will be associated with all forms and documents related to a single valid Rapid SARS-CoV-2 Antigen test result.

The NP swab collection will not provide participants additional training because the collection technique differs from AN collection. Participants will be reminded that the study representative is performing a different collection technique for a different test and that the participant should refer only to the instructions for use for the proper collection technique.

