The Clinical Investigators or designees will observe AN swab collection and testing and ensure that the nasopharyngeal swab comparator PCR specimens from each participant are properly collected according to the protocol. NP samples will be collected according to the Interim Guidelines for Collecting, Handling, and Testing Clinical Specimens for COVID-19 using materials approved for use with CDC 2019-nCoV Real-Time RT-PCR Diagnostic Panel (CDC) provided by DMH Premier including synthetic tip swabs with a plastic or aluminum shaft and VTM, UTM, or PBS transport media. Subjects will collect AN swab samples and perform

the Rapid SARS-CoV-2 Antigen Test using only the IFU (Appendix 7) or instructional video (link contained within the IFU) for instruction. The collection devices and storage tubes will be appropriately labeled with the study ID numbers and not the names of the participants to maintain confidentiality. The same unique study ID number will be applied to all forms and sample(s) associated with a single Rapid SARS-CoV-2 Antigen Test Card valid result.

Following Rapid SARS-CoV-2 Antigen Test, subjects will complete a questionnaire gauging user comprehension of results and consequences of performing the Rapid SARS-CoV-2 Antigen test incorrectly (Appendix 5). Replacement Rapid SARS-CoV-2 Antigen Test Cards will be provided to re-test invalid results. Repeated results will be noted.

Qualified personnel will follow instructions for collection of CDC 2019-nCoV Real-Time RT-PCR Diagnostic Panel (CDC) used by DMH Premier for comparator nasopharyngeal swab sample collection and shipment (Appendices 1 and 2).

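### Protocol 4.0 sets only a minimum gap between the NP comparator and the antigen swab and can be read to admit a pre-enrolment comparator; it should be reconciled with 1.3 and 4.3, which describe a same-visit swab

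*Protocol*

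**What the plan says.** Protocol 4.0 describes the comparator as a standard-of-care NP sample, taken at least 15 minutes before the antigen sample, "with at least 15 minutes between nasal collections including collections that may occur prior to study enrollment". On place and order it adds: "Comparator SOC samples will be collected first by qualified personnel at a study site or physician's office". Recruitment is by internet and by referral.

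Other text describes a comparator taken within the study:

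- Protocol 1.3: "a Study Representative will collect and ship a second nasopharyngeal swab sample for comparator PCR testing".
- Protocol 4.0, later in the same section: "All specimens will be collected from participating consenting subjects".
- Protocol 4.3 on consent: "Specimens will be collected and tested only after the Informed Consent form is completed".
- Protocol 4.3 on the visit: participants are told that the study representative's NP technique differs from their own. Investigators or designees are to "ensure that the nasopharyngeal swab comparator PCR specimens from each participant are properly collected according to the protocol", and tubes carry the study ID.

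The device "detects SARS-CoV-2 viral antigens through visual interpretation of color development" (1.4). Its acceptance criteria include "Positive Percent Agreement (PPA) greater than or equal to eighty percent" (2.2), alongside NPA of at least 98%.

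**The concern.** A method comparison assumes that both tests see the same infection state and that one result does not influence the other. A minimum gap protects the second swab from disturbance by the first. It does nothing to keep the two swabs close in time.

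If 4.0 is read to allow a comparator taken before enrolment, two things could go wrong in the affected pairs. Viral load could change between swabs, so a disagreement would reflect timing and not the device. The subject, tester or observer could also already know the PCR result when judging a faint line by eye. Either could shift PPA or NPA, and the two effects need not act in the same direction. The point matters because these pairs would feed directly into the figures judged against the acceptance criteria.

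**Working it through.** The plan gives no figure for this point, so there is none to reproduce. The check is textual, with one short calculation for scale.

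**1. What 4.0 fixes.** It fixes the order of collection (NP first) and a gap of at least 15 minutes. It gives no upper limit.

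**2. The two readings of the pre-enrolment clause.**

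- *Comparator reading:* the NP swab may itself predate enrolment. In favour: the standard-of-care label, the physician's-office location, recruitment by referral, and the explicit mention of collections before enrolment.
- *Spacing reading:* the clause only makes a subject wait 15 minutes after any earlier nasal swab. In favour: the consent wording in 4.0 and 4.3, the study representative taking the NP swab (1.3, 4.3), and collection according to the protocol (4.3).

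The spacing reading has more support, but no sentence states it. Same-visit collection is an inference; no section uses those words.

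**3. Whether another rule would catch an old or known-result pair.**

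- *Maximum interval:* none in the protocol or the SAP.
- *Order of results:* Protocol 5.9 has the antigen test read at collection, and 5.6 ships the NP swab overnight. A same-visit PCR result would therefore normally arrive later. That follows from logistics and is not a stated rule. Protocol 5.11 reports the PCR result to the subject and/or provider without saying when.
- *Eligibility:* Protocol 4.5 excludes prior medical or laboratory training and prior self-collection or self-testing. A staff-collected NP swab with a known result is not covered.
- *Data exclusion:* Protocol 6.2.1 and 6.2.2, and the matching SAP paragraphs, remove invalid runs only. A valid antigen result paired with a valid but older PCR result stays in.

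**4. Scale.** Inputs: at least 30 PCR positives and 30 PCR negatives (Protocol 4.4); PPA at least 80% and NPA at least 98% (Protocol 2.2).

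- Weight of one read among n positives = 100/n points. At n = 30: 100/30 = 3.3 points.
- 24/30 = 80.0% meets the PPA criterion; 23/30 = 76.7% does not.
- At 30 negatives, one false positive gives 29/30 = 96.7%, below 98%.

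These figures show how much one affected pair could matter at the minimum counts. They do not estimate how many such pairs there would be; the documents give no basis for that number. The SAP also mentions a total of 188 subjects without saying how many are PCR positive. With more than 30 positives, each read weighs less than 3.3 points.

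**The case against.** The strongest reply is that the protocol already closes the harmful reading. A comparator swabbed before consent would breach both 4.0 and 4.3. The reminder to participants in 4.3 presupposes a study representative taking the NP swab with the participant there. A routine earlier swab would not ordinarily have been taken under the investigator's oversight or carry a study ID. The grammar of 4.0 also points to a spacing rule: the comparator-to-antigen gap is set first, so the further clause adds something only if it covers other nasal swabs. Overnight shipping then puts the PCR result after the antigen read.

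Most of this stands, and it is why the exposure is only conditional. It does not settle the matter. The consent wording sits beside a clause that contemplates collections before enrolment, consent and enrolment are not defined as the same moment, and neither passage sets an upper interval. Shipping time protects the read only when the swab is taken at the visit.

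It is also fair to say that the appendix forms, the SOPs or the FDA template that 4.0 follows may already set these rules. Those were not available here, so the gap is in the protocol and SAP text only.

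A reader might go further and infer that the study will use days-old comparators, that testers will know the PCR result, or that PPA will be inflated. The documents support none of these. No passage says that an earlier swab will be used, the described workflow points the other way, and a timing gap could as easily lower PPA as prior knowledge could raise it.

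**Conclusion.** The point holds as an ambiguity that needs reconciling. Protocol 4.0 sets only a lower bound and can be read to admit a pre-enrolment comparator. Protocol 1.3 and 4.3 describe a study-collected swab after consent with the participant present. Nothing in the protocol or SAP limits the interval, fixes the order of results, or removes an affected pair from the acceptance PPA and NPA.

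The consequence is conditional. It is nil if every comparator is taken at the same visit. If some are older, size and direction are unknown, because neither the number of such pairs nor the effect in each can be derived from the documents. The only firm scale is one read: 3.3 PPA points at 30 positives, enough to decide the criterion at the boundary. This is a minor-to-moderate fix, worth making before collection because pairs without recorded timing may not be separable afterwards.

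**What to change.** - In Protocol 4.0, state that the pre-enrolment clause is a spacing rule for earlier nasal swabs and that the comparator is collected at the same visit, or within a stated short window. Align this with 1.3 and 4.3.
- Require the antigen result to be recorded before the PCR result is available to the subject, tester or observer.
- If earlier swabs are to be allowed as comparators, record both collection times and any prior knowledge of the PCR result. In the SAP, report out-of-window or known-result pairs separately from the acceptance PPA and NPA.
- If an appendix, SOP or the cited template already contains these rules, a citation in 4.0 is enough.

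The cost is a few sentences. If earlier swabs are allowed, add two time fields and one yes/no field where the forms lack them. The downside is that a few previously swabbed referrals may not count, which could slightly slow accrual of PCR positives.

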#### 4.1 Site Characteristics

All personnel involved in the study will be qualified by education and experience to conduct this study and agree to follow the study protocol.

#### 4.2 Site Personnel

Each site in this evaluation is responsible for assignment of qualified personnel and for maintaining documented required qualifications for those personnel.

#### 4.3 Specimen Collection

Each study volunteer who agrees to participate in the study will be asked to complete an Informed Consent Form (Appendix 7). A parent or guardian will need to consent for subjects under 18 years old. Study subjects between the ages of 7 and 13 years old will be asked to complete an age-appropriate Assent form (Appendix 8). Study subjects between ages 14 and 17 will complete the assent portion of the Informed Consent Form (Appendix 7). Minors between the ages of 2 and 13 years old will have their samples collected and tested by a parent or legal guardian. Minors between the ages of 14 and 17 will collect and test their own samples without interference from their parents or legal guardians. Specimens will be collected and tested only after the Informed Consent form is completed.

Each testing participant will be asked to complete a tester information form assessing basic demographics and socio-economic questions (Appendix 3). Each subject being tested will be asked to complete a subject information form describing any symptoms of respiratory illness and/or resent exposure to confirmed COVID-19 positive individuals within the last two weeks (Appendix 4). If the tester is self-collecting, then they skip the second half of the subject information form as indicated on the form due to redundancy of demographic and socio-economic information recorded on the tester information form. Subjects and testers will be observed by EDP Biotech Corp. personnel or designees during sample collection and testing process in person. The same unique study ID number will be associated with all forms and documents related to a single valid Rapid SARS-CoV-2 Antigen test result.

The NP swab collection will not provide participants additional training because the collection technique differs from AN collection. Participants will be reminded that the study representative is performing a different collection technique for a different test and that the participant should refer only to the instructions for use for the proper collection technique.

The Clinical Investigators or designees will observe AN swab collection and testing and ensure that the nasopharyngeal swab comparator PCR specimens from each participant are properly collected according to the protocol. NP samples will be collected according to the Interim Guidelines for Collecting, Handling, and Testing Clinical Specimens for COVID-19 using materials approved for use with CDC 2019-nCoV Real-Time RT-PCR Diagnostic Panel (CDC) provided by DMH Premier including synthetic tip swabs with a plastic or aluminum shaft and VTM, UTM, or PBS transport media. Subjects will collect AN swab samples and perform

the Rapid SARS-CoV-2 Antigen Test using only the IFU (Appendix 7) or instructional video (link contained within the IFU) for instruction. The collection devices and storage tubes will be appropriately labeled with the study ID numbers and not the names of the participants to maintain confidentiality. The same unique study ID number will be applied to all forms and sample(s) associated with a single Rapid SARS-CoV-2 Antigen Test Card valid result.

Following Rapid SARS-CoV-2 Antigen Test, subjects will complete a questionnaire gauging user comprehension of results and consequences of performing the Rapid SARS-CoV-2 Antigen test incorrectly (Appendix 5). Replacement Rapid SARS-CoV-2 Antigen Test Cards will be provided to re-test invalid results. Repeated results will be noted.

Qualified personnel will follow instructions for collection of CDC 2019-nCoV Real-Time RT-PCR Diagnostic Panel (CDC) used by DMH Premier for comparator nasopharyngeal swab sample collection and shipment (Appendices 1 and 2).

